**C. Subject Selection****Inclusion criteria**

1. Patient must be willing and able to give informed assent/ consent for participation in the study
2. Patient must be willing and able (in the PI's opinion) to comply with all study requirements.
3. Patient must be a premenopausal female over the age of 18.
4. Patient must have a documented history of IBS that is not completely controlled by current IBS drugs.
5. Patient must have a score of  $\geq 150$  on the IBS-SSS at screening.
6. Patient must have no clinically relevant (in the judgment of the PI) abnormal blood laboratory levels at screening or randomization.
7. The clinician will assess eligibility as per the Rome IV criteria (Recurrent abdominal pain or discomfort at least 1 day/week in the last 3 months associated with two or more of the following: Improvement with defecation. Onset associated with a change in frequency of stool).

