### B1. PURPOSE OF PROTOCOL

Irritable bowel syndrome (IBS) is a chronic functional gastrointestinal disorder that is commonly seen in clinical practice. Specifically, it is a functional bowel disorder that is thought to result from a disorder of gut–brain interaction. Though patients with IBS often have a heterogeneous symptom profile, the predominant theme is the presence of abdominal pain or discomfort that is usually relieved by defecation. Genetic background and environmental factors are important in the pathogenesis of IBS, but the precise cause of IBS is still unknown.

Probiotics are live microorganisms with a vast array of therapeutic potential for gastrointestinal disease. Several probiotics strains have shown beneficial outcomes in constipation-predominant IBS (IBS-C) patients, especially as an adjunct to conventional treatment. However, a number of controversial issues regarding the roles of probiotics in pathogenesis of IBS-C remain to be clarified, including precise mechanism of action.

This protocol aims to assess the impact of a mix of 24-beneficial strains on fecal metagenomic stability and individual gastrointestinal symptoms specifically in a cohort of subjects with IBS-C or IBS-M.

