### B3. DESCRIPTION OF RESEARCH PROTOCOL

#### A. Study Design – Overview, Methods, Procedures

##### Study Design

This is a 1:1 randomized, double blind 12-week comparison of effects of SH-DS01 by Seed Health Inc. versus placebo, in a cohort of 100 women with IBS with constipation or IBS with mixed bowel habits. 50 IBS-C or IBS-M patients will receive the daily synbiotic for 12 weeks, while 50 IBS-C or IBS-M patients will receive the placebo.

- **Initial Screening Session (1 hour)** – The purpose of this screening is to determine if the subject meets the qualifications to participate in the research study. After the screening is complete they will be notified whether they meet qualification or not. If the subjects qualify they will be provided with the supplementation and instructions for future study appointments. Informed Consent: This will be explained by a member of the study staff in an individual setting. After it has been explained and all questions have been answered, the subject will be asked to sign the consent form.

- Brief Medical History Form: After completing this short survey, the medical history will be reviewed and either approval will be issued to continue with the study or exclusion from further participation.
- Physical Exam:
  - Measurement of Height, Weight: the subject will be asked to remove shoes and any items in pockets (i.e. loose change, wallet, watch, cell phone, etc.) prior to having height (stadiometer) and weight (digital scale) measured.
- Medical history and interval history to include current medications, recording of adverse events (including intercurrent illness and any new diagnoses).
- Other Vital Signs: Temperature, Heart Rate, Blood Pressure
- **Study Procedures for Qualified Participants:** If the subject meets the study requirements and is cleared for study enrollment they will be asked to complete the following tasks:
  - **Pre-supplement wash-out (1 week):** during which the participant is to stop taking probiotics or antibiotics, in order to eliminate any residual effects of the synbiotic intervention. During this period, subjects will be provided with a single blinded placebo. Participants who are judged to be “responders” will be excluded from further participation in the trial.

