**B. Statistical Considerations****Statistical analysis**

This study is a randomized, double-blind, placebo-controlled trial comparing study subjects treated with a daily synbiotic vs. placebo. We will perform all statistical tests all under the null hypothesis that there is no difference between the two groups (synbiotic and placebo) against the two-sided alternative that they are not equivalent. Analyses will be conducted using an Intention to Treat (ITT) analysis and will include all study subjects who are randomized into this trial. Study subjects who drop out of the study will be considered failures for subsequent outcomes.

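### Inclusion criterion 7 asks for two or more features but lists only two, so the list appears incomplete and does not clearly match the Rome IV criteria that the same sentence cites

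*Combined protocol and SAP*

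**What the plan says.** The trial is to be run "in a cohort of 100 women with IBS with constipation or IBS with mixed bowel habits" (B3, Study Design). The symptom-based diagnosis rests on inclusion criterion 7 under C. Subject Selection, which has two parts in one sentence.

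- **A reference to an external standard:** "The clinician will assess eligibility as per the Rome IV criteria".
- **A parenthesis that spells out a rule:** recurrent pain or discomfort on at least one day a week over the last three months, "associated with two or more of the following: Improvement with defecation. Onset associated with a change in frequency of stool". The parenthesis closes there.

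No other section gives a further associated feature or a different threshold. Of the neighbouring criteria, number 4 asks for a documented history of IBS that current drugs do not fully control, and number 5 asks for an IBS-SSS score of at least 150 at screening. Neither deals with the features that accompany the pain. The documents do not reproduce the Rome IV criteria.

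**The concern.** A requirement for at least two items from a list makes sense only if the list has three or more. Here it has two. Either an item was dropped in drafting, or both features were meant to be required and the wording is wrong. The text does not say which.

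The sentence also gives the clinician two authorities, the named standard and the printed list. If the standard contains any feature that the parenthesis omits, the two can give different answers for the same woman, and nothing in the protocol says which prevails. At stake are consistent eligibility decisions, the loss of some candidates who would qualify under the cited standard, and the ability of a monitor to check afterwards which rule was used.

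**Working it through.** The plan gives no figure to reproduce, and no sample size, power or alpha enters. The check is a count of yes/no feature patterns.

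**Inputs**
- Threshold: at least 2 features (inclusion criterion 7).
- Features printed: 2, improvement with defecation and onset with a change in stool frequency (same criterion).
- Length of the full list, k: not in the documents. k = 3 and k = 4 are assumptions, used only to show the logic, and both suppose that the full list contains the two printed features.

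**Formulas**
- Patterns in total: 2^k.
- Patterns that pass at least 2 of k: 2^k − 1 − k (all patterns, less the one with no feature and the k with exactly one).
- Patterns that contain both printed features: 2^(k−2).
- Patterns that pass the full list but fail the printed one: the second count minus the third.

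| k | Patterns | Pass at least 2 of k | Contain both printed features | Pass full list, fail printed list |
|---|---|---|---|---|
| 2 (as printed) | 4 | 4 − 1 − 2 = 1 | 1 | 0 |
| 3 (assumed) | 8 | 8 − 1 − 3 = 4 | 2 | 4 − 2 = 2 |
| 4 (assumed) | 16 | 16 − 1 − 4 = 11 | 4 | 11 − 4 = 7 |

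**Reading the table**
1. As printed, only 1 of 4 patterns passes, the one with both features. The words *or more* do no work.
2. If one item is missing, 2 of the 4 qualifying patterns fail the printed list. Each is one printed feature plus the omitted one.
3. If two items are missing, 7 of the 11 qualifying patterns fail the printed list. One of them consists of the two omitted features alone.
4. For every k, a pattern with exactly one feature fails the threshold of two. Lengthening the list does not change that.
5. For every k, a woman with both printed features also meets at least two of the longer list. On this point the short list can only be stricter.

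These are counts of patterns, not proportions of women. Turning them into proportions would need the prevalence of each feature and how the features occur together, and the documents give neither.

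**The case against.** The strongest reply is that the operative instruction is to assess by Rome IV and that the parenthesis is only a gloss. Recruitment draws on a centre for functional bowel disorders and on gastroenterology referrals (B6), where clinicians may well apply the standard from knowledge and pass over a truncated list. This stands in part: exclusion of women who qualify is a possible result, not an established one. It does not remove the defect, because a clinician who follows the printed text can decide otherwise and the protocol does not say which part governs.

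A second reply is that an item may have been lost when the PDF was read. The capsule composition list in B3 shows a single prebiotic where B2 names three, so lists in this copy can be short. The closing parenthesis and full stop make that less likely here, but it cannot be ruled out entirely.

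Third, the criterion acts before randomisation and equally on both arms. This stands in full.

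A reader might also infer more than the documents support:
- **That women with only one feature are wrongly excluded.** They fail a threshold of two whatever the length of the list, and nowhere do the documents say that one is enough.
- **That the enrolled women could not be described as meeting the criteria.** On the feature count the reverse holds: anyone with both printed features meets two or more of any longer list that contains them.
- **That the criterion contradicts the protocol's own account of IBS,** since B1 describes "the presence of abdominal pain or discomfort that is usually relieved by defecation". That is background on the condition, and a trial may enrol a narrower group.
- **That the missing item is stool form.** B2 mentions stool consistency and hard stools when it reports earlier studies of single strains. Those reports do not establish what belongs in this diagnostic list.

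**Conclusion.** The point holds as an inconsistency within one eligibility criterion. The threshold and the list do not fit each other, and the printed rule cannot be assumed to match the standard it cites. Read literally, both features are mandatory. The women affected would be those who reach the threshold through a feature that is not printed.

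The size cannot be established. The number and identity of any missing items are not in the documents, no feature prevalences are given, and it is unknown which half of the sentence clinicians would follow. The conclusion that women could be lost assumes that the cited standard has at least one associated feature beyond the two printed, which the words *or more* suggest but do not prove. The consequence is limited to inconsistent screening and lost recruits. The randomised comparison of synbiotic with placebo is not biased by it.

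**What to change.** Reconcile the parenthetical list and its threshold with the Rome IV criteria that the sentence cites, so that one rule governs eligibility. The sponsor should work from the source itself, since the documents do not show what, if anything, was dropped. Add a tick list to the screening form on which the clinician records the associated features each woman meets, so that decisions can be checked and the enrolled group described feature by feature.

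The cost is one sentence in the protocol, a few boxes on a form and a minor amendment. No procedure or visit is added. If women have already been screened under the present wording, the amendment should be dated so that those screened before and after it can be told apart.

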**Exclusion criteria**

1. Patient has clinically significant unstable medical conditions other than IBS.
2. Patient has had clinically relevant symptoms or a clinically significant illness in the four weeks prior to screening or randomization.
3. Patient has clinically significant laboratory values (in the PI's opinion).
4. Patient has a history or presence of alcohol or substance abuse within the last two years prior to the study or daily consumption of five or more alcohol-containing beverages.
5. Patient is currently using or has in the past used recreational or medicinal cannabis, or synthetic cannabinoid based medications (including Sativex®) or supplements (including hemp oil/extracts) within one month prior to study entry and is unwilling to abstain for the duration for the study.

6. Patient has consumed any probiotic product three days prior to screening and/or is unwilling to abstain from consuming these during the study.
7. Intake of antibiotics in the past 1-month (i.e. penicillin, amoxicillin, cephalexin (Keflex), erythromycin (E-Mycin), clarithromycin (Biaxin), azithromycin (Zithromax), ciprofloxacin (Cipro), levofloxacin (Levaquin), ofloxacin (Floxin), co-trimoxazole (Bactrim), trimethoprim (Proloprim), tetracycline (Sumycin or Panmycin), doxycycline (Vibramycin), gentamicin (Garamycin), or tobramycin (Tobrex). The supplement in the present study may have a minor interaction with these medications.
8. Patient has any known or suspected hypersensitivity to pomegranate, pine, or mushrooms, or any of the excipients of the Supplement Synbiotic Product (SSP).
9. Patients of child bearing potential unless willing to ensure that they use effective contraception, for example, oral contraception, double barrier, intra-uterine device, during the study and for three months thereafter.
10. Patients who are pregnant, lactating, or planning pregnancy during the course of the study and for three months thereafter.
11. Patients who have been part of a clinical trial involving any investigational product in the previous six months.
12. Any other significant disease or disorder which, in the opinion of the PI, may either put the patient at risk because of may either put the patient at risk because of participation in the study, may influence the result of the study, or affect the patient's ability to participate in the study.
13. Following a physical examination, the patient has any abnormalities that, in the opinion of the investigator would prevent the patient from safe participation in the study.
14. Patients unwilling to abstain from donation of blood during the study.
15. There are plans for the patient to travel outside the USA during the study.
16. Obesity (BMI > 30)
17. Implantable device such as heart pacemaker.
18. Patients unwilling to abstain from donation of blood during the study.
19. History of inflammatory bowel disease.
20. History of diverticulosis.
21. History of cardiovascular disease.
22. History of kidney/liver/serious infection.
23. History of diabetes or other hormone diseases.
24. History of abdominal surgery.
25. Currently suffering from high blood pressure.
26. Following a physical examination, the patient has any abnormalities that, in the opinion of the investigator would prevent the patient from safe participation in the study.
27. There are plans for the patient to travel outside the USA during the study.

#### **B4. POSSIBLE BENEFITS**

No direct benefit to subjects is expected.

**B5. POSSIBLE RISKS AND ANALYSIS OF RISK/BENEFIT RATIO**

The possible risks for the study include risks of the symbiotic, typical blood drawing risks and risks to taking questionnaires.

Synbiotic

Side effects are transient bloating, loose stools, gas and diarrhea. Also, a rare allergic reaction to pomegranate.

Blood Drawing

The risks and discomforts of blood drawing from a vein include the possibility of pain or bruising at the site of the blood draw; occasional feeling of lightheadedness; and rarely, infection at the site of the blood draw.

Surveys/Questionnaires

Some of the questions asked as part of this study may make the subject feel uncomfortable.

**B6. RECRUITMENT AND CONSENT PROCEDURES****Recruitment**

Patients will be identified in the following ways:

- Clinical practice of the Center for Functional Bowel Disorders and GI Motility at BIDMC
- GI referrals from BIDMC
- Review of medical records, data repositories, and appointment logs
- Clinical Query 2
- Advertisements

Potential study participants (obtained from the means listed above) will be contacted by phone and a brief phone screening will be initiated to assess subject's eligibility before scheduling the office visit.

Potential study participants identified through Clinical Query 2 or appointment logs will be mailed a letter or postcard with opt-in information.

**Consent**

During the screening visit the Investigator will fully explain the purpose of the study to the patient and all questions and concerns regarding the study will be addressed as well (informed consent process) in a private area in the Division of Gastroenterology.

**Subject Protection**

None of the subjects in this study will be vulnerable to coercion or undue influence

**B7. STUDY LOCATION****Privacy**

All data will be kept in a password protected folder on the BIDMC shared drive. All blood and stool samples will be coded without patient identifiers and stored in keycard protected floors in research areas at BIDMC. When the mucosal samples will be sent to outside collaborators/labs, they will not have any PHI labeled.

**Physical Setting**

All samples will be stored in freezers on keycard protected floor 6 of Dana at BIDMC. All data generated from this study will also be stored in password protected folder of BIDMC shared drive.

**B8. DATA SECURITY**

All data will be kept in a password protected folder on the BIDMC shared drive. Serum, urine and mucosal samples will be labeled without patient identifiers.

## **B9 Multi-Site Studies**

Is the BIDMC the coordinating site? ☐ Yes ☒ No

Is the BIDMC PI the lead investigator of the multi-site study? ☐ Yes ☒ No

## **B10 Dissemination of Research Results**

Patients will not be informed about the results of the study. Results might be presented/published.
